Morphologic Relapse after CR/CRi/CRpa	Defined as one of the following conditions: 
 
Reappearance of <math>\geq 5\%</math> blasts in the BM not attributable to any other cause (eg, BM regeneration after consolidation therapy); or
 
Development of extramedullary disease
 

Not evaluable (NE)a	Defined as without a posttreatment response assessment
Stable Disease (SD)a	Defined as failure to meet any of the above criteria and not meeting the criteria of progressive disease (see below)
Progressive Disease (PD)a	Defined as one of the following conditions: 
 
For subjects with 5 to 70% BM blasts at baseline: a <math>> 50\%</math> increase of BM blast count percentage from baseline to <math>\geq 20\%</math>; or
 
For subjects with <math>> 70\%</math> BM blasts at baseline: a doubling of absolute blast count in peripheral blood from baseline to <math>\geq 10 \times 10^9/L</math> (10,000/<math>\mu</math>L); or
 
Development of new extramedullary disease since last response assessment
 
 Progressive disease is to be confirmed by 2 consecutive response assessments separated by at least 1 month. The date of progressive disease is defined as the first date that one of three conditions listed above was met.

AML = Acute Myeloid Leukemia; ANC= Absolute Neutrophil Count; BM= Bone Marrow; IWG= International Working Group.

a Modification to IWG response criteria. Note: CRh is not available for the investigator's assessment and will be assessed by the Sponsor only and based on laboratory dataset.

b If the pre-treatment bone marrow blast percentage was 50% to 100%, the percentage of blasts must decrease to a value between 5% and 25%; if the pre-treatment blast percentage was 20% to less than 49%, they must decrease by at least half to a value of more than 5%.

Notes: Deletions to the IWG response criteria are not shown.

Source: [Cheson, 2003](#).

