10.3.1.2. Event-Free Survival

Event-free survival (EFS) is defined as the period from the date of randomization to the date of documented morphologic relapse (hereafter referred as relapse) after CR/CRi/CRp, PD according to modified IWG AML response criteria or death from any cause, whichever occurs first. Subjects who are alive without any of these events will be censored at the date of their last valid response assessment. Subjects who do not have post-randomization response assessment will be censored at date of randomization.

If a subject begins a new anti-cancer therapy prior to documented disease progression (or death), the subject will be censored at the date of last assessment before starting the new anti-cancer therapy. Subjects with two or more consecutive missing response assessments prior to documented progression (or death) will be censored at the last date of response assessment before the missing assessments.

Analysis of EFS will be similar to the analysis of OS. The stratified log-rank test based on the ITT population will be considered the primary analysis for EFS, with unstratified analyses and the analyses based on mITT populations considered supportive analyses. The analysis based on local assessment of response will be conducted as a supportive analysis of EFS.

Additionally, EFS will be repeated for a Dose group analysis of AG-221 subjects who had at least one dose > 100mg during the study versus those who received only dose ≤100mg.

Table 4: Censoring Rules for EFS

Value of Event-free Survival Date (ADT)	Censored (Y,N)	Derivation
ADT = min(death date, relapse date, progression date)	N	If a subject died, relapsed, or had disease progression by independent review, and the subject has less than two consecutive missing response assessments prior to a visit documented death, relapse, or progression which is before any subsequent anti-cancer therapies
ADT = the last event-free assessment date before missing assessments/ randomization date	Y	If a subject died, relapsed, or had disease progression by independent review, and the subject has two or more consecutive missing response assessments prior to a visit documented death, relapse, or progression
ADT = the last assessment date/randomization date	Y	If a subject did not die, or did not have relapse or progression, and did not receive any subsequent anti-cancer therapies. If there was no post-randomization response assessment, then ADT = the randomization date.

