15.5. International Working Group Acute Myeloid Leukemia Response Criteria

Hematologic Response According to modified IWG Criteria for AML	
Category	Definition
Morphologic Complete Remission (CR)	Defined as less than 5% blasts in a BM aspirate sample with marrow spicules and with a count of at least 200 nucleated cells. There should be no blasts with Auer rods and absence of extramedullary disease. Plus, all the following conditions should be met: 
 ANC $\geq 1 \times 10^9/L$ (1,000/μL) Platelet count $\geq 100 \times 10^9/L$ (100,000/μL) Independent of red cell transfusions for ≥ 1 week immediately before each response assessment
Morphologic Complete Remission with Incomplete Neutrophil Recovery (CRi)^a	Defined as all criteria of morphologic CR except the following: 
 ANC $< 1 \times 10^9/L$ (1,000/μL)
Morphologic Complete Remission with Incomplete Platelet Recovery (CRp)^a	Defined as all criteria of morphologic CR except the following: 
 Platelet count $< 100 \times 10^9/L$ (100,000/μL)
Morphologic Complete Remission with Partial Hematologic Recovery (CRh)^a	Defined as all criteria of morphologic CR except the following: 
 ANC $> 0.5 \times 10^9/L$ (500/μL), and Platelet count $> 50 \times 10^9/L$ (50,000/μL)
Morphologic Leukemia-free State (MLFS)	Defined as less than 5% blasts in a BM aspirate sample with marrow spicules and with a count of at least 200 nucleated cells. There should be no blasts with Auer rods and absence of extramedullary disease
Partial Remission (PR)	Defined as all hematologic criteria of morphologic CR with a $> 50\%$ decrease in the percentage of BM blasts to 5% to 25% (a blast count value of $< 5\%$ may also be considered a partial remission if Auer rods are present) ^b
Cytogenetic Complete Remission (CRc)	Defined as CR/CRi/CRp with a reversion to a normal karyotype in cases with an abnormal karyotype at baseline, based on evaluating ≥ 20 metaphase cells from BM
Morphologic Relapse after CR/CRi/CRp^a	Defined as one of the following conditions: 
 Reappearance of $\geq 5\%$ blasts in the BM not attributable to any other cause (e.g., BM regeneration after consolidation therapy); or Development of extramedullary disease
Not evaluable (NE)^a	Defined as without a post-treatment response assessment

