Stable Disease (SD)^a	Defined as failure to meet any of the above criteria and not meeting the criteria of progressive disease (see below)

Progressive Disease (PD) ^a	
Defined as one of the following conditions:
 
 • For subjects with 5 to 70% BM blasts at baseline: a > 50% increase of BM blast count percentage from baseline to $\geq 20\%$; or • For subjects with > 70% BM blasts at baseline: a doubling of absolute blast count in peripheral blood from baseline to $\geq 10 \times 10^9/L$ (10,000/μL); or • Development of new extramedullary disease since last response assessment 
Progressive disease is to be confirmed by 2 consecutive response assessments separated by at least 1 month. The date of progressive disease is defined as the first date that one of three conditions listed above was met.

--	---

AML = Acute Myeloid Leukemia; ANC= Absolute Neutrophil Count; BM= Bone Marrow; IWG= International Working Group.

^a Modification to IWG response criteria.

^b If the pre-treatment bone marrow blast percentage was 50% to 100%, the percentage of blasts must decrease to a value between 5% and 25%; if the pre-treatment blast percentage was 20% to less than 49%, they must decrease by at least half to a value of more than 5%.

Notes: Deletions to the IWG response criteria are not shown.

Source: [protocol Appendix F](#).

15.6. Hematologic Improvement According to the International Working Group for Myelodysplastic Syndromes

Hematologic Improvement According to IWG Criteria	
Hematologic improvement ^a	Response criteria (responses must last at least 8 week) ^b
Erythroid Response (HI-E) (pre-treatment, < 11 g/dL)	
 Hemoglobin increase by ≥ 1.5 g/dL Relevant Reduction in units of RBC transfusions by an absolute number of at least 4 RBC transfusions/8 week compared with the pretreatment transfusion number in the previous 8 weeks 
Note: Only RBC transfusions given for a hemoglobin of ≤ 9.0 g/dL on treatment will count in the RBC transfusion response evaluation ^b

Platelet Response (HI-P) (pre-treatment, < $100 \times 10^9/L$)	
 Absolute increase of $\geq 30 \times 10^9/L$ for subjects starting with $> 20 \times 10^9/L$ platelets Increase from $\leq 20 \times 10^9/L$ to $> 20 \times 10^9/L$ and by at least 100% ^b

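### Subjects with 66.67–70% baseline marrow blasts and no CR, CRi or CRp cannot be scored as progressing on blast counts, because the marrow criterion would need more than 100% and the blood criterion starts above 70%

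*SAP*

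**What the plan says.** SAP 15.5 lists three conditions, any one of which is PD.

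- Marrow: "For subjects with 5 to 70% BM blasts at baseline: a > 50% increase of BM blast count percentage from baseline", with the follow-up value at 20% or more. Protocol Appendix F opens the same condition with the same range: "For subjects with 5 to 70% BM blasts at baseline".
- Blood: "For subjects with > 70% BM blasts at baseline: a doubling of absolute blast count in peripheral blood from baseline", with the follow-up count at 10 x 10^9/L or more.
- Extramedullary: "Development of new extramedullary disease since last response assessment". This has no baseline restriction.

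PD needs confirmation at a second assessment a month or more later. Stable disease is the residual category. Both documents mark the PD definition as a modification of the published criteria.

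Relapse is a separate category that exists only after CR, CRi or CRp. It is met by a return of 5% or more "blasts in the BM not attributable to any other cause", or by extramedullary disease, whatever the baseline.

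SAP 10.3.1.2 dates the EFS event at "documented morphologic relapse (hereafter referred as relapse) after CR/CRi/CRp, PD according to modified IWG AML response criteria or death from any cause", whichever comes first. It censors a subject who starts new anti-cancer therapy before an event at the last assessment before that therapy. SAP 10.3.2.1 ends duration of response at relapse, PD or death. Protocol 4.2 sets a floor of 5% marrow blasts for entry and no ceiling.

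**The concern.** A criterion based on a proportional rise in a percentage runs out of room as the baseline approaches the ceiling. The blood criterion supplies a measure for high baselines, but it is opened above 70%, and the marrow criterion stops being attainable before that. Subjects between the two points can be enrolled and are left without a usable blast-based definition of progression.

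EFS is the second key secondary endpoint in the alpha-controlled sequence (Protocol 9.6, SAP 10.1). In this band, blast progression without remission is not an event. If the subject then starts new anti-cancer therapy, EFS is censored after a real progression, so the censoring may be informative. Duration of response has a narrower problem: for a responder whose best response is PR or MLFS, relapse is not defined and PD cannot be reached on blasts.

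**Working it through.** **Inputs.** Marrow criterion: baseline 5–70%, rise of more than 50%, follow-up at least 20%. Blood criterion: baseline above 70% (both from SAP 15.5 and Protocol Appendix F). Planned enrolment: 316 (Protocol 4.1). The 70% switch is a stated definition, so there is no derived figure in the plan to reproduce.

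**Step 1: where the marrow criterion stops being attainable.** A relative rise of more than 50% requires follow-up > 1.5 x baseline. Follow-up cannot exceed 100%, so the criterion is attainable only if 1.5 x baseline < 100, that is baseline < 100/1.5 = 66.67%.

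| Baseline marrow blasts | Follow-up needed | Marrow criterion attainable | Blood criterion open |
|---|---|---|---|
| 50% | > 75% | yes | no |
| 60% | > 90% | yes | no |
| 65% | > 97.5% | yes, barely | no |
| 66% | > 99% | yes, barely | no |
| 66.67% | > 100% | no | no |
| 68% | > 102% | no | no |
| 70% | > 105% | no | no |
| above 70% | not applicable | not applicable | yes |

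The gap is 70 - 66.67 = 3.33 percentage points. If blasts are recorded in steps of 0.5%, as a 200-cell count would give, the closed values are 67.0, 67.5, 68.0, 68.5, 69.0, 69.5 and 70.0%.

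**Step 2: which events remain for a subject in the band.**

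| Situation | EFS event | Duration-of-response event |
|---|---|---|
| Blast return after CR/CRi/CRp | yes, relapse | yes, relapse |
| New extramedullary disease | yes, PD | yes, PD |
| Death | yes | yes |
| Blast rise, no response reached | no | not in the analysis |
| Blast rise after PR or MLFS only | no | no |

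The defect lies in the last two rows. There the EFS date moves to death, or the subject is censored when new therapy begins.

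**Step 3: how many subjects.** The documents give no baseline blast distribution, and the SAP 8.2.1 table will not show the band because its top category is 50% and above. Under assumptions:

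- Uniform over 5–100%: 3.33/95 = 3.5%; 0.035 x 316 = about 11 subjects.
- 1% in the band: 0.01 x 316 = about 3. 6% in the band: 0.06 x 316 = about 19.

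These count everyone in the band. Misclassified progressions are fewer: the subject must also have no CR/CRi/CRp, progress on blasts without new extramedullary disease, and live to the confirming assessment.

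**The case against.** The strongest reply is that the effect is small. The band is 3.33 points wide, the rule is the same in both arms, and the IRAC is blinded. EFS is tested only if overall survival and overall response rate both succeed, and neither of those uses PD. With planning medians of 5.6 and 8 months for survival, many affected subjects would still have an EFS event at death soon afterwards. The SAP also plans EFS sensitivity analyses that lift the censoring at new therapy. Most of this stands. The sensitivity analyses, however, recover only a later death; they do not restore the missed progression date.

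The IRAC charter, which the SAP cites for response procedures, is not among the documents and may already deal with the gap. That does not repair SAP 15.5, which states the definition itself.

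A reader might infer more than the documents support in four ways.

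- That progression in this band is never an EFS or duration-of-response event. It is one through relapse after CR/CRi/CRp, extramedullary disease or death.
- That the EFS comparison is diluted. Nothing in the documents allows the size or direction of any effect on the hazard ratio to be estimated. The amendment rationale says control subjects may receive commercial AG-221, so censoring at new therapy could differ by arm, but in which direction cannot be established.
- That the gap reaches down to 60%. Between 60% and 66.67% the marrow criterion is demanding but attainable.
- That the 50% means percentage points, which would close the marrow criterion from 50% upward. The wording describes a rise from baseline and is most naturally relative. It would still help to say so.

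**Conclusion.** Wrong as written. In both documents the marrow criterion is arithmetically unattainable from 66.67% to 70% baseline blasts, and the blood criterion applies only above 70%. Subjects in this band without CR, CRi or CRp and without new extramedullary disease cannot be scored PD on any rise in marrow or blood blasts. For them the EFS event is delayed to death or lost to censoring, and a PR or MLFS response cannot end by blast progression.

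The arithmetic rests only on reading the 50% as relative. The count rests on an assumed blast distribution: about 11 of 316 under a uniform spread, about 3 to 19 under shares of 1–6%, with fewer actual misclassified events. Overall survival and overall response rate are untouched. This is a limited defect in the event definition of an alpha-controlled endpoint, and it is worth correcting because the correction is simple.

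**What to change.** For IRAC scoring of EFS and duration of response only, reconcile the two baseline ranges in SAP 15.5, and in the IRAC charter if it does not already do so, so that every baseline value has an attainable blast-based criterion. On the relative reading, the existing blood criterion must be available from no higher than 66.67%. State that the 50% rise is relative to baseline. Record the departure from Protocol Appendix F in SAP Section 13, report the number of subjects with baseline blasts in the band, and present EFS under the current wording as a sensitivity analysis.

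This should not alter how PD is used in treatment rules. Protocol 7.2.1.2 and 11.1 also rely on PD, for dose modification and treatment discontinuation. The sponsor should reconcile those passages with Appendix F separately.

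The cost is a short edit to the SAP and possibly the charter, using central marrow and blood data already collected. A few subjects would have an earlier EFS event. The definition would change after the March 2019 interim analysis, so the edit must be made and dated before the final database lock.
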